Patients who have completed the washout period and the 2-day urinary diary (*completed by the patient or parent/caregiver*) will have a baseline urodynamic evaluation performed at Visit **B** (Baseline Visit, Week 0 of treatment). **Patients** will be enrolled in the study following the urodynamic measurements. **Patients** will report back to the clinic for scheduled visits at Weeks **2**, **6**, **10**, **and 14** (\pm 2 days) as detailed **below**.

Eligible *patients* will begin treatment *the morning after Visit B (Week 0 of treatment)* with 0.75 g of gel/day. This will be the start of the *14*-week treatment period, and *followed by* 4 additional visits, on Weeks 2, *6*, *10*, and *14* of treatment.

At Visit *C* (Week 2 of treatment), a blood sample will be collected for *PK* analysis. *After study assessments at* Visit *C are completed*, the daily dose may be adjusted up to 1 g/day, down to 0.5 g/day, or remain the same at 0.75 g/day. The determination of dose will be based on the investigator's clinical judgment and assessment of the patient's bladder symptoms and treatment side effects. *Patients* will remain on this dose until the end of the *treatment* period.

A 2-day urinary diary will be completed prior to Visit D, and urodynamic assessments will be performed at Visit D (Week 6 of treatment). A blood sample for PK analysis will also be collected at Visit D.

Safety will be evaluated during the *14*-week *treatment* period by monitoring adverse events *(AEs)*, vital signs, *and* clinical laboratory evaluations, and *by assessing* skin erythema at the most recent application site.

Other evaluations will include a 12-lead electrocardiogram (ECG) at screening and an anticholinergic symptoms questionnaire at *Visits C, D, E, and F*.

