9.3.1 Inclusion Criteria

Patients will be considered for inclusion in the study if they meet all of the following criteria:

- IN01. Are 3 years-of-age (6 years for Pre-Amendment 3) to < 17 years-of age, at the time of screening

- IN02. Have a diagnosis of detrusor overactivity associated with a neurological condition
- IN03. Are using CIC
- IN04. Are capable of completing the urinary diary with or without assistance from a parent or guardian
- IN05. Have correctly completed the baseline urinary diary
- IN06. Are capable of understanding and complying with the study requirements, are willing to provide assent to participate in the study as required by the institutional review board or ethics committee, and the parent(s) or legal guardian(s) have been adequately informed and have signed the informed consent/authorization to disclose PHI
- IN07. For children < 8 years, have completed vision assessments within 12 months prior to the Screening Visit. If a child does not have a vision assessment performed within the last 12 months, it will be acceptable if it is performed by a trained healthcare professional (trained nurse, technician, or physician) at the study site or a separate site during the Screening or Baseline Visit (Appendix 8).

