	values at an analysis visit (e.g., Week 6 LOCF)
	 Estimates derived from a model for CFB value controlling for factors (treatment
	group) and covariates (baseline value)
	Least squares (LS) means and standard errors
	LS mean differences, and 95% confidence intervals for oxybutynin chloride
	gel vs Placebo
	 P-values from contrast t-test comparing oxybutynin chloride gel vs Placebo
	N1 = portioinants with non-missing values at both baseline and the specific 1
	• N1 = participants with non-missing values at both baseline and the specified postbaseline analysis visit
Exact (Clopper-	Exact 95% CI for a single proportion
Pearson) 95% CI	Exact 9370 CI for a single proportion
1 carson, 75/0 Cl	

SAP OG09002 Oxybutynin Chloride 10% Gel

Methodology	Description
Exact	• Exact 95% CI for difference between two proportions
unconditional 95%	
CI using the score	
statistic	
Cochran-Mantel-	P-value from CMH test controlling for baseline covariates
Haenszel (CMH)	
Kolmogorov-	P-value from exact Kolmogorov-Smirnov test to examine whether two distributions
Smirnov test	are the same

CFB = change from baseline; ANCOVA = analysis of covariance.

Raw and derived data listings will be provided, and will be fully defined in the table, figure, and data listing specification document.

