Volume at first involuntary detrusor contraction	Change from baseline to Week 6 (or LOCF)	Pre-Amendment 3 Week 6 (LOCF) of double-blind period; Post-Amendment 3 Week 6 (LOCF) of open-label period; Combined ITT (LOCF)	CFB ANCOVA Pre- Amendment 3; CFB one-sample t-test Post-Amendment 3; CFB ANCOVA for Combined ITT
Presence (versus total absence) of involuntary detrusor contractions at > 15 cm H2O	Raw value at Week 6 (or LOCF)	Pre-Amendment 3 Week 6 (LOCF) of double-blind period; Post-Amendment 3 Week 6 (LOCF) of open-label period; Combined ITT (LOCF)	CMH test Pre-Amendment 3; Exact 95% CI Post-Amendment 3; CMH test for Combined ITT

¹ Weeks are defined in Section 6.2.1.

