5.2.2 Changes to Analyses Prior to Database Lock

Version	Date	Summary
1.0	24 Oct 2017	Original version
2.0	28 Mar 2022	 Exact (Clopper-Pearson) 95% CI, Exact unconditional 95% CI using the score statistic, and Cochran-Mantel-Haenszel (CMH) was added in Table 5-2 to analyze binary urodynamic variable (Presence (versus total absence) of involuntary detrusor contractions at > 15 cm H2O)
		 CFB Mixed Model was deleted from Table 5-2. All CFB Mixed model analyses have been replaced with CFB ANCOVA as reflected in Table 5-12
		 Study part was removed as a factor from the CFB ANCOVA models
		 Details of how urodynamic assessments will be analyzed have been added in Table 5-12
		 Section 5.1.1.2 was modified to clarify analysis populations presented in demographics tables.
		 Exact Kolmogorov-Smirnov test was added in Table 5-2 to compare whether distributions of efficacy endpoints between patients treated with oxybutynin chloride gel in the two parts (Pre-Amendment 3 and Post-Amendment 3) of the study are the same
		 Section 5.1.1.3.1 was modified to provide details on how efficacy endpoints will be analyzed based on whether the distributions of efficacy endpoints between patients treated with oxybutynin chloride gel in the two parts (Pre- Amendment 3 and Post-Amendment 3) of the study were the same or not
		 Updated Table 5-15 definition of treatment-emergent adverse events in double-blind period to distinguish between participants who enter the 8-week open-label period from those that do not

6. Data Handling and Analysis Conventions

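### In the Post-Amendment 3 part, presence of involuntary detrusor contractions is the only urodynamic measure analysed without reference to baseline, so within-child change is neither tabulated nor tested

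*SAP*

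**What the plan says.** The last row of SAP Table 5-12 (section 5.1.1.3.1) covers the presence or total absence of involuntary detrusor contractions above 15 cm H2O. The analysed quantity is "Raw value at Week 6 (or LOCF"), and the methods are "CMH test Pre-Amendment 3; Exact 95% CI Post-Amendment 3; CMH test for Combined ITT". SAP Table 5-2 defines the Clopper-Pearson entry as "Exact 95% CI for a single proportion". The choice is deliberate: the change log in SAP 5.2.2 says that exact intervals and CMH were added in version 2.0 "to analyze binary urodynamic variable (Presence (versus total absence) of involuntary detrusor contractions at > 15 cm H2O").

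The other four urodynamic rows of Table 5-12 analyse change from baseline, with "CFB one-sample t-test Post-Amendment 3".

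Both measurements needed for a paired analysis are collected. Under Protocol 9.1, children who have finished washout and the diary "will have a baseline urodynamic evaluation performed at Visit" B, and "urodynamic assessments will be performed at Visit D (Week 6 of treatment"). SAP Table 5-11 defines a baseline for the urodynamic parameters.

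Protocol 11.7.4 adds descriptive summaries by visit for the Post-Amendment 3 safety population, with frequency distributions for categorical urodynamic variables. Its change-from-baseline summary covers only the continuous ones.

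**The concern.** The Post-Amendment 3 part has no comparator, so within that part a pharmacodynamic response has to be judged against each child's own baseline. The SAP does this for four of the five urodynamic measures and not for the fifth.

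A Week 6 proportion could stand alone only if every child were known to have such contractions at entry. The entry criteria do not ensure that. Inclusion criterion IN02 reads "Have a diagnosis of detrusor overactivity associated with a neurological condition", and no criterion asks for a contraction above 15 cm H2O at Visit B. The baseline proportion could therefore be well below 100%.

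Pharmacodynamics is part of the stated secondary objective. What is at stake is whether the report can say, for this measure, how many children changed on gel and with what precision.

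**Working it through.** **Figures in the plan.** Neither document gives an expected rate, a power or a precision figure for this endpoint. The only power figures (93%, and 90% after dropout) concern the primary diary endpoint of the randomised design and do not bear on this point. The inputs from the documents are n = 25 (the minimum Post-Amendment 3 enrolment, SAP 5.1.2) and two-sided 95% intervals (SAP 5.1.1.1.3). All counts below are assumptions for illustration.

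**Step 1: the SAP output.** Suppose 15 of 25 children show contractions at Week 6. The planned result is 15/25 = 60%, with a Clopper-Pearson 95% CI of 38.7% to 78.9%. Baseline status does not enter the formula, so the result is the same for any baseline.

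**Step 2: what the interval leaves open.** Let b be the number who lose contractions and c the number who gain them. The exact McNemar p-value is min(1, 2 × P(X ≤ min(b, c))), with X binomial (b + c, 0.5). For the same 15/25 at Week 6:

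| Present at baseline | Lost (b) | Gained (c) | Exact McNemar p |
|---|---|---|---|
| 25/25 | 10 | 0 | 0.002 |
| 22/25 | 8 | 1 | 0.039 |
| 20/25 | 6 | 1 | 0.125 |
| 15/25 | 2 | 2 | 1.0 |
| 8/25 | 0 | 7 | 0.016 (worsening) |

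**Step 3: add the by-visit frequencies of Protocol 11.7.4.** The baseline proportion is now visible, and the rows of that table can be told apart: 22/25 to 15/25 reads as 88% to 60%, and 15/25 to 15/25 as 60% to 60%. With complete pairs the two frequencies fix b − c but not b and c separately. For 22 at baseline and 15 at Week 6, b − c = 22 − 15 = 7. Only 25 − 22 = 3 children can gain contractions, so c runs from 0 to 3:

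| Lost (b) | Gained (c) | Exact McNemar p | Converted among 22 present at baseline (95% CI) |
|---|---|---|---|
| 7 | 0 | 2 × 1/128 = 0.016 | 32% (14% to 55%) |
| 8 | 1 | 2 × 10/512 = 0.039 | 36% (17% to 59%) |
| 9 | 2 | 2 × 67/2048 = 0.065 | 41% (21% to 64%) |
| 10 | 3 | 2 × 378/8192 = 0.092 | 45% (24% to 68%) |

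Where the two frequencies are equal, b = c and p = 1.0 whatever the split.

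**Step 4: what a paired test could detect.** At n = 25, with 5% gaining contractions, the power of the exact McNemar test is 17%, 46%, 72% and 89% if 20%, 30%, 40% and 50% lose them.

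**The case against.** The strongest reply is that the planned outputs, taken together, are not blind to baseline. Protocol 11.7.4 already gives frequencies by visit, and the SAP describes itself as expanding the protocol's statistical section. Its change log does not say that those summaries were dropped. This stands, and it limits the point. A reader of Table 5-12 alone might infer that the plan cannot distinguish many children losing contractions from none doing so. That is true of the Week 6 interval taken alone, but not of the interval together with the by-visit frequencies. What remains missing is the split into losses and gains and any measure of its uncertainty. The frequencies are also planned for the safety population, whereas the SAP bases pharmacodynamic analyses on ITT.

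Second, these children also enter the Combined ITT CMH test against placebo in the same row, so the endpoint does have a comparator in the study as a whole. This also stands. That comparison is not randomised for them, however, and it does not describe change within the single arm.

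Third, the SAP promises raw and derived listings and keeps its table specifications in a separate document. With about 25 children, change could be read by hand from a listing, and a shift table in the other document cannot be ruled out. A listing is still not a pre-specified summary.

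Fourth, a reader might infer that a paired test would show an effect of gel. It would not: without a concurrent control it shows change and not its cause. The same limit applies to the one-sample t-tests planned for the other four measures, so it is no reason to treat this one differently.

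**Conclusion.** The point holds, and it is limited. For one of five urodynamic measures, the Post-Amendment 3 analysis in Table 5-12 makes no use of the baseline value. The protocol's by-visit frequencies supply the two proportions but not the change between them. Under the assumed counts (25 complete pairs, 22 present at baseline, 15 at Week 6), this leaves the paired p-value undetermined between 0.016 and 0.092, and the conversion proportion between 32% and 45%.

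The sizes are illustrative, because the documents give no contraction rates and 25 is a minimum enrolment rather than a number of paired assessments. The finding itself rests only on the text of Table 5-12, Table 5-2 and Protocol 11.7.4, and on the absence of a contraction requirement at entry.

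It would go too far to say that the pharmacodynamic objective cannot be met, since the other four measures have change-from-baseline tests. Neither the primary conclusion nor any diary-based secondary conclusion changes. The sponsor should still correct the row, because the data are already collected and the other urodynamic rows show the intended approach.

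**What to change.** In the last row of Table 5-12, keep the Week 6 exact interval and add three items for the Post-Amendment 3 ITT population:

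- A two-by-two shift table of presence at Visit B by presence at Week 6. Table 5-2 already defines a shift analysis that can be adapted.
- An exact McNemar test on the discordant pairs.
- The proportion converting from present to absent among children with contractions above 15 cm H2O at Visit B, with its Clopper-Pearson 95% CI.

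State the number of children with both assessments. Add a sentence saying that the result describes within-child change on gel and is not a controlled treatment effect.

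The cost is a few lines of SAP text and one additional table, with no new data collection. The downside is one more secondary p-value with modest power at n = 25 (46% if 30% lose contractions and 5% gain them). The shift table and the conversion proportion with its interval should therefore carry most of the interpretation.

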5.1.1.4 Safety Analyses

Safety analyses will be based on each safety population.

Baseline assessments for applicable safety endpoints defined as follows:

Table 5-13 Safety Endpoint Baseline Definitions

Parameter	Description	Timing
Clinical laboratory evaluations	eCRF- or (standardized) vendor-provided	Latest non-missing
 Vital signs 	assessments	assessment
 Physical Examination 		on/before treatment
Skin Assessments for		start date
Erythema		

5.1.1.4.1 Study Treatment Exposure and Compliance

Study treatment exposure and compliance will be summarized by treatment group or oxybutynin chloride gel level, as applicable, and by visit and overall for each safety population as follows:

Table 5-14 Study Treatment Summaries

Parameter	Description	Timing	Methodology
Study treatment	Date of last dose of the study drug minus Date of	Study Period	Continuous
exposure (days)	first dose of the study drug + 1	within a	descriptives
		Study Part ¹	
Categorical study	Number and percentage of participants exposed	Study Period	Categorical
treatment exposure	to treatment during each of the following	within a	descriptives
	intervals:	Study Part ¹	
	• Week (0, 1]		
	• Week (1, 2]		
	• Week (2, 3]		
	• Week (3, 4]		
	• Week (4, 5]		
	• Week (5, 6]		
	• Week (6, 7]		
	• Week (7, 8]		
	• Week (8, 9]		
	• Week (9, 10]		
	• Week (10, 11]		
	• Week (11, 12]		
	• Week (12, 13]		
	• Week (13, 14]		
	• Week >=14		
Study treatment	Summary by period interval	Study Period	Continuous
compliance (%)	Pre-Amendment 3:	within a	descriptives
	100 × # of sachets dispensed – # returned	Study Part ¹	

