9.2 Rationale for Study Design and Control Group

Prior to Amendment 3, this study was designed as a double-blind, placebo-controlled study followed by an open-label safety extension, with a total planned enrollment of approximately 96 patients and the expectation that a minimum of 25 evaluable pediatric patients would complete the open-label extension period and provide long-term (14-week) safety data for oxybutynin chloride gel in pediatric patients.

Six weeks of treatment is sufficient

to observe a treatment effect. The additional 8 weeks of open-label treatment *was intended to* increase the number of patient exposures to oxybutynin chloride gel and generate long-term safety data. *Post-Amendment 3 enrollment, the open-label treatment will allow for further ascertainment of efficacy and safety data for oxybutynin chloride gel in pediatric patients.* The use of urinary diaries will generate *data* for assessment of primary and secondary endpoints in this study. *Assessment of* urodynamics is a *customary* and accepted method to measure changes in bladder function with oxybutynin and other anticholinergic agents.^{9,10} The percent*age of* catheterizations without leakage is a clinically meaningful endpoint, and catheterization volume *is an accepted* surrogate measure of changes in bladder capacity.

Safety monitoring for this study, including physical examination, vital signs, clinical laboratory measurements, and skin erythema assessments, are evaluations previously used to evaluate the safety of transdermal oxybutynin in pediatric *patients*. *Post-Amendment 3, vision assessment prior to or at the Baseline Visit was added for patients < 8 years old and a vision symptom questionnaire for all patients was added to monitor visual changes.*

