11.6.2 Extent of Exposure

Summaries for duration of exposure for *each* safety population will be provided by treatment group for the *Pre-Amendment 3 double-blind* period, and by exposure to *oxybutynin chloride gel* for *each of* the *Pre-Amendment 3 and Post-Amendment 3 open-label* periods *and the Pre-Amendment 3 double-blind* and *open-label* periods combined. Duration of exposure to study *treatment* will be summarized using descriptive statistics (mean, 25th percentile, median, 75th percentile, SD, SEM, minimum, maximum, and number of *patients*). Duration of exposure will be calculated as the difference between the last dose date and the first dose date plus 1 day.

Additionally, these summaries will present the number and percentage of *patients* for each interval (1-week multiples) of total exposure. The denominators for calculating the percentages will be based on the number of *patients* with exposure.

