4.1 Study Design Summary

This study was initiated as a double-blind, placebo-controlled study with an open-label extension and was amended via protocol amendment (Protocol Amendment 3) to enroll participants under only open-label treatment. Therefore, analyses are described with respect to prior to protocol amendment 3 ("pre-amendment 3") and with protocol amendment 3 ("post-amendment 3").

Prior to Amendment 3, participants aged 6 years to < 17 years who had a diagnosis of detrusor overactivity associated with a neurological condition and were using clean intermittent catheterization (CIC) to control bladder function were randomly assigned 1:1 to receive doubleblind oxybutynin chloride gel or placebo gel for 6 weeks. Enrollment was stratified based on sex, age, and weight. Stratification was done within the following groups: male and female; 6 to < 12 years-of-age and 12 to < 17 years-of-age; and by weight category: ≤ 25.0 kg and > 25.0 kg for the 6 to < 12 years-of-age group and \le 50.0 kg and > 50.0 kg for the 12 to < 17 years-of age group. Enrollment into the 6-week treatment period was to be followed by an open-label, 8-week period to generate safety data. All participants began treatment with 0.75 g of gel/day for 2 weeks. Participants then returned to the clinic at Week 2 for a potential dose titration and at this time their dose could have been adjusted up to 1 g/day, down to 0.5 g/day, or remained the same at 0.75 g/day. The determination of dose was based on the investigator's clinical judgment and assessment of the patient's bladder symptoms and treatment side effects. Dose titration was permitted only once during the entire 6-week double-blind, placebo-controlled period. Participants continued blinded treatment for 4 additional weeks until the end of the double-blind treatment period.

Post-Amendment 3, the study became a multicenter, open-label, dose-titration study in pediatric participants, ages 3 years to < 17 years, with detrusor overactivity associated with a neurological condition. A minimum of 25 participants are to be enrolled. Efforts will be made to enroll a greater number of participants from the ages of 3 years to < 6 years. Participants must be suitable

[figure not shown]

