	# expected		

¹ Study part refers to pre-amendment 3 and post-amendment 3; pre-amendment 3 has both open-label and double-blind periods, post-amendment 3 has only open-label period.

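### SAP Table 5-14 omits, undeclared, the summary Protocol 11.6.2 requires of gel exposure across both Pre-Amendment 3 periods, so it shows no Pre-Amendment 3 patient with 14 weeks of gel

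*SAP*

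**What the plan says.** Protocol Section 11.6.2 asks for duration of exposure at three levels: by treatment group in the Pre-Amendment 3 double-blind period; by gel exposure in each open-label period; and by gel exposure across the two Pre-Amendment 3 periods joined, in its words "periods *and the Pre-Amendment 3 double-blind* and *open-label* periods combined". It gives one formula: "Duration of exposure will be calculated as the difference between the last dose date and the first dose date plus 1 day". It also asks for counts in one-week intervals of total exposure.

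SAP Section 5.1.1.4.1 uses the same formula (it ends "first dose of the study drug + 1") and introduces its table with "chloride gel level, as applicable, and by visit and overall for each safety population as follows". In Table 5-14, the Timing entry for both the continuous and the categorical exposure row is the study period within a study part. Footnote 1 explains the term: "pre-amendment 3 has both open-label and double-blind periods, post-amendment 3 has only open-label period". The weekly intervals end with Week (13, 14] and then Week >=14.

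SAP Table 5-1 defines four safety populations: Pre-Amendment 3 double-blind, Pre-Amendment 3 open-label, Post-Amendment 3 open-label, and the two open-label populations combined. SAP Section 5.2 sends the reader to Section 5.2.2 for changes from the protocol's planned analyses. Nothing there concerns exposure.

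**The concern.** The open-label extension was added to lengthen exposure. Protocol Section 9.2 records the expectation under the original design that "a minimum of 25 evaluable pediatric patients would complete the open-label extension period and provide long-term (14-week) safety data". A patient randomised to gel who completed both periods is the only kind of Pre-Amendment 3 patient with 14 weeks on gel. If exposure is reported only one period at a time, that patient is split into two shorter records, and the exposure tables understate how long Pre-Amendment 3 children were treated.

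The omission looks unintended. The SAP keeps the joined double-blind and open-label periods for erythema (Section 5.1.1.4.6) and for the anticholinergic questionnaire (Section 5.1.1.5.1). It also keeps a double-blind-to-gel sequence grouping for laboratory data and vital signs (Sections 5.1.1.4.3 and 5.1.1.4.4). Exposure, the natural companion to those safety summaries, has no such link.

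A smaller matter sits in the same table: the top two intervals share a boundary at exactly 14 weeks, which is the planned Post-Amendment 3 treatment length.

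**Working it through.** **Inputs**

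- Double-blind period: "oxybutynin chloride gel or placebo gel for 6 weeks" (SAP Section 4.1), so 6 × 7 = 42 days.
- Pre-Amendment 3 open-label period: "open-label, 8-week period to generate safety data" (SAP Section 4.1), so 8 × 7 = 56 days.
- Exposure = last dose date − first dose date + 1 (Protocol Section 11.6.2; SAP Table 5-14).
- Weekly intervals as listed in SAP Table 5-14.

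**The plan's own figure.** Protocol Section 9.2 speaks of 14-week data. 6 + 8 = 14 weeks, or 42 + 56 = 98 days, which agrees.

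**A completer on gel in both periods**, with double-blind dosing on days 1 to 42 and open-label dosing on days 43 to 98:

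| Summary | Days | Weeks | Table 5-14 interval |
|---|---|---|---|
| Double-blind only | 42 − 1 + 1 = 42 | 6.0 | (5, 6] |
| Open-label only | 98 − 43 + 1 = 56 | 8.0 | (7, 8] |
| Both joined, as the protocol requires | 98 − 1 + 1 = 98 | 14.0 | (13, 14] and also >=14 |

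Table 5-14 as written produces the first two rows and not the third.

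**A completer on placebo and then gel.** Gel exposure is 56 days, or 8.0 weeks, whether or not the periods are joined, because the 6 placebo weeks are not gel exposure.

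**Do late or early visits change this?** Assume each period's last dose moves by 4 days either way; the documents give no such figure for Pre-Amendment 3. The double-blind period then runs 38 to 46 days (5.4 to 6.6 weeks) and the open-label period 52 to 60 days (7.4 to 8.6 weeks). To pass 13 weeks the open-label period alone would need 92 days, an overrun of 92 − 56 = 36 days. To reach 14 weeks it would need 98 days, an overrun of 98 − 56 = 42 days. Ordinary visit timing does not put a Pre-Amendment 3 patient in the top intervals.

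**Can another SAP population supply the figure?** None of the four in Table 5-1 joins blinded gel to later open-label gel. The combined open-label population joins Pre- and Post-Amendment 3 patients, not a patient's two periods.

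**Interval boundary.** 98 / 7 = 14.0 satisfies both 13 < weeks ≤ 14 and weeks ≥ 14. If each patient belongs in one interval of total exposure, a patient with exactly 98 days has two.

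**The case against.** **The summary has not been withdrawn.** A reader might infer that the SAP has dropped it, so that no patient with continuous gel treatment can ever be counted. The documents do not go that far. The SAP says it expands the protocol's statistical section, Section 5.2.2 records no change to exposure, and the table specifications are in a separate document not available here. What stands is an undeclared omission: the protocol still asks for the summary and the SAP does not specify it.

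**The SAP has wording that seems to cover both periods.** The introduction to Section 5.1.1.1.1 describes, as an example, a Pre-Amendment 3 safety population whose members took blinded treatment and may also have taken open-label gel. Table 5-1 does not define that population, it would include placebo patients, and the per-period timing would still apply. The word overall in the lead-in to Table 5-14 is paired with visits, so it does not override the Timing column.

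**Timing cells in this SAP are not always complete.** This is fair: the Timing cell of Table 5-21 lists only Post-Amendment 3 visits, although its prose also covers the Pre-Amendment 3 periods. For exposure, however, neither the prose nor the cell names the joined periods. In Table 5-16, where a wider span is wanted (the combined open-label period), the Timing cell names it.

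**The shared boundary may be harmless.** Table 5-14 refers to patients exposed during each interval, which could mean counting a patient in every week reached. Multiple counting would then be intended. The protocol's reference to intervals of total exposure favours one interval per patient, but the point is minor and affects only patients with exactly 98 days.

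**Exposure is descriptive.** No test or decision rule depends on it, and the figure could be derived later from dosing dates. This limits the weight of the point but does not remove the mismatch.

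**Conclusion.** The point holds as an undeclared mismatch between Protocol Section 11.6.2 and SAP Table 5-14. Followed as written, the table shows each Pre-Amendment 3 patient treated with gel in both periods as about 6 weeks and about 8 weeks, and shows no Pre-Amendment 3 patient with 14 weeks of gel. This rests on the planned period lengths and on reading the Timing column with its footnote as the specification.

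Two stronger readings are not supported. First, 14-week exposure is not lost altogether. Post-Amendment 3 patients have a single 14-week period, so Table 5-14 can capture the expected minimum of 10 patients with 14 weeks of exposure (Protocol Section 11.1; SAP Section 5.1.2). Second, a reader might take the original expectation of 25 extension completers, halve it for 1:1 allocation (25 / 2 = 12.5), add the 10, and conclude that about 22 patients would be reported as 10. The 25 was an expectation for a design since amended, and the documents give no Pre-Amendment 3 enrolment or completion figures. The size of the understatement is therefore unknown.

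The correction is worth making before database lock, but it affects a descriptive safety table and no efficacy conclusion.

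**What to change.** In SAP Table 5-14, add a continuous row and a weekly-interval row for gel exposure over the Pre-Amendment 3 double-blind and open-label periods combined. Specify that:

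- only gel days count, so a patient randomised to gel starts at the first double-blind dose and a patient randomised to placebo starts at the first open-label dose;
- any gap between the last double-blind and first open-label dose is handled by a stated rule, because last minus first plus 1 would otherwise count the gap as treatment.

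Change the last interval from Week >=14 to Week >14, so that exactly 98 days falls only in (13, 14].

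Pooling this row with Post-Amendment 3 patients would be informative, but the protocol does not require it and it can be left optional. If the sponsor prefers not to produce the combined summary, the omission and its reason should be recorded in Section 5.2.2.

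Table 5-14 already needs the dosing dates, so the cost is a SAP wording change and a little programming time.
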